Acceptance of FACE among African-American families has been high. 6,9,56 Among African-Americans living with HIV (n=192), 91% in the FACE intervention completed an advance directive, while only 15% in the control had completed an advance directive. 107 Study findings may increase equity in pACP, recognized by the Centers for Disease Control as minimizing suffering, 104 and improving public health. 108 Study outcomes are related to the National Consensus Project domains for palliative care: 109 psychological (emotional health, caregiver strain, caregiver distress), social (positive caregiving appraisals, family well-being), and spiritual (meaning/peace) and attend to the cultural and ethical domains of care. 110-113 There is an ethical imperative to engage in pACP, ¹¹⁴ despite the real concerns about the emotional impact, ^{56,115-117} because these conversations may actually support hope. 118-122 A.2.b. Development, Feasibility & Beta Testing of Integrated 4-session FACE-Rare. Our team developed and beta-tested the integrated FACE-Rare intervention at Children's National. 41 Of 9 families approached, 8 enrolled and 7 completed baseline. All 7 children had total parenteral nutrition (TPN) and 5 were wheelchair bound. All family caregivers were mothers and 43% African-American. Of the 6 mothers who began Session 1, 100% completed all 4 sessions and the 2week follow-up assessment. The most frequently rated support need for their child, "Knowing what to expect in the future when caring for my child." Satisfaction ratings demonstrate 100% reported the sessions were useful and helpful, while half felt sad talking about goals of care. Two African-American fathers participated in creating advance care plans. This is significant as male caregivers are rarely studied. 123 They have agreed to participate in the Community Advisory Board to increase male caregiver participation in FACE-Rare. See Letters of Support. Average time to complete questionnaires was 27 minutes and families reported no respondent burden. 124 Findings demonstrate feasibility and acceptability. Families who participated in the development and beta-testing will not be eligible to participate in this R21. Parents reported, "Dealing with perpetual grief" and "Living on the precipice." Overall impact is high because findings will improve scientific knowledge of clinical practice supporting family caregivers whose children experience high rates of mortality 125 change to Specific Aims number and may decrease family caregiver strain, associated with higher overall mortality for family caregivers of older adults. 125

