minutes each is comprised of the CSNAT approach [Sessions 1 & 2] and Respecting Choices [Session 3]. Investigators will test the initial efficacy of FACE-Rare on measurable outcomes at baseline and 3-months post-intervention. See **D5** for description of intervention. See **Power Analysis** for rational for 30 dyads. D.2. Study Population. Nearly half of all pediatric inpatients in tertiary hospitals suffer from life-threatening diseases, and of these 82% have rare diseases. 139 A profile of children in the last year of life revealed that 56% had multiple complex chronic conditions. 139 For this reason investigators will include children with multiple-morbidities and include the large proportion of children with rare diseases treated in tertiary hospitals who are unable to communicate because of age, untreatable communication disorder, or intellectual disability. If multiple family caregivers participate, data will only be used for the primary caregiver, as determined by the couple. However, data will be collected from all participants for secondary analysis. Child inclusion criteria are (1) ≥1.0 years and <18.0 years at enrollment; (2) unable to participate in end-of-life care decision-making; (3) have a rare disease as operationally defined (See Human Subjects); (4) not under a Do Not Resuscitate Order or Allow a Natural Death Order; and (5) not in the Intensive Care Unit. Family caregiver inclusion criteria are: (1) > 18.0 years at enrollment; (2) legal guardian of child and child's caregiver; (3) can speak and understand English; (4) not known to be developmentally delayed; and (5) not actively homicidal, suicidal or psychotic at the time of enrollment. Investigators will collect data on reasons for declining. D.2.a. Study Site. Children's National has an internationally recognized clinical genetics program, which records over 8,000 patient visits a year. The Children's National Rare Disease Institute is the first of its kind, focused exclusively on advancing the care of children with rare diseases. Eligible families will be enrolled from Children's National (N=32 dyads). Based on previous research, 5-9,56 investigators estimate 50% of families approached will agree to enroll, and 1% will be ineligible at secondary screening. So to achieve our randomization goal of 30 family/child dyads investigators will need to approach 32 families, which is realistic. **D.3. Recruitment and Retention Plan.** Recruitment will use principles of inclusiveness. Investigators recognize that disease progression may impact enrollment and will take steps to accommodate caregivers. See Human Subjects and. Investigators will recruit during clinic visits, but not on day of diagnosis. The site's

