
team is experienced and will use methods described by rare disease researchers.⁴ Recruitment Procedures: Investigators will use a two-step recruitment procedure that ensures involvement of the primary provider or medical care team and reduces the potential burden to families. To minimize gatekeeper bias, prior to study initiation, investigators will conduct educational forums to discuss the study and address the legitimate reasons for providers to refuse approach. First, the study team will identify potential patients through review of future appointments. Second, the health care provider will confirm eligibility criteria, e.g. patient does have a rare diagnosis and the condition is not a result of prematurity, such as in pulmonary hypertension. The health care provider will let the study team know if there is a reason not to approach the family. Third, a trained member of the study team will approach the family by email and/or telephone, and/or text, as long as COVID-19 prevents face-to-face approaches. The selection, roles, responsibilities, and preparation of families are detailed in the 3-day Protocol Training. "Because of COVID-19 and the difficulty with face-to-face recruitment posed by the epidemic, we are requesting to ADD to our recruitment strategy a modified form of Snowball Recruitment. 1. Potential participants will be contacted by previous participants (from the beta testing phase of our study in 2019) who are currently members of our Community Advisory Board (CAB). We are asking them to tell other people about the study. The CAB member will use the IRB approved flyer to describe the study to other people (family caregivers of children with rare diseases, whose child receives care at Children's National, and whose child is between the ages of 1 up to age 18) who may be eligible. If interested these people will contact the researcher directly using the researchers' contact information on the IRB approved Flyer. This approach will protect patient privacy. 2. We will not be doing "cold calling." 3. CAB members will not be receiving any compensation for providing referrals or be offered incentives to provide referrals. 4. Current participants will not be required to refer others or incur any penalty for not referring other participants. 5. The CAB member do not have power over the potential participants, such as an employeremployee relationship, but may be members of various advocacy groups that support family caregivers." Consent and Enrollment: Family caregivers will undergo written informed consent using IRBapproved documents prior to participation in any study procedures or data collection. Investigators have IRB approval for a waiver of assent for the children, as one eligibility criterion is "unable to participate in healthcare decision making." Randomization and Blindness: Randomization will be triggered by computer following completion of the baseline assessment in the already established REDCap database. Employing an intent-totreat paradigm, dyads will be randomly assigned to FACE-Rare vs. TAU at a ratio of 1:1. The FACE-Rare

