H3a: FACE-Rare families will have a significant higher probability of completing pediatric Advance Care Planning (pACP) documents for their child, compared to controls. Difference in the odds of completing pACP documents at 3-months post-intervention between intervention groups will be first examined using two-sided Fisher's exact test and then exact logistic regression)^{159,160} will be applied to examine the intervention effect on the odds of completing pACP, controlling for covariates (age, gender, race). H3b: FACE-Rare families will have a significant higher probability of having pACP documents locatable in the electronic health record, compared to controls. The analytical approaches proposed for testing H3a will be applied for testing H3b. Exploratory AIM. To evaluate the initial efficacy of FACE-Rare on child healthcare utilization (hospitalization, surgeries, and ER visits etc.), compared to controls. Previous studies suggest few cases in this brief time period, so descriptive statistics by intervention group without test will be reported with future plans to estimate costs associated with pACP. Power & Sample Size Consideration. Based on previous FACE research, 5,8,56 a sample size of 30 dyads will be sufficient to find statistically and clinically meaningful differences at 3 monthspost intervention and provide an effect size for a future R01. With attrition at 15%, 25-26 dyads will be available at 3-months post-intervention. With a small sample, the quality of the standard errors, parameter coverage, the power of detecting effects, and the quality of overall tests of fit may be in question. However, parameter estimates are often dependable even through sample size is small. Having realized the small sample size, we have proposed Fisher's exact tests, exact logistic regression, and particularly Bayesian for statistical tests and modeling. As such, the proposed study would provide useful information about the effect size that will be used to power a future R01. Investigators may not have sufficient power to report sex differences for caregivers. However, we will report our findings separately by sex in progress reports and publications. **D.10. Brief Timeline.** Investigators received IRB approval and completed the initial REDCap data base. Months 0-3: hire, train & certify project staff. Months 4-23: Ongoing recruitment, enrollment, assessments/data collection, fidelity monitoring, data cleaning. Months 23-24: Analysis and dissemination. See Study Timeline. **D.11. Alternative Strategies** We will only study staff willing to work flexible hours and to inconvenience themselves to meet families' scheduling needs. Weekly meetings will allow for early trouble shooting. If underenrolled, investigators will use CTSI-CN Power Trials to identify additional eligible children/families and/or add a study site. We will actively recruit fathers/male caregivers. See Recruitment and Retention Plan. Future Plans: If R21 aims are achieved, a future multi-site R01 will test the full theoretical model to improve pACP for children with rare diseases and their caregivers through family engaged pACP.¹⁶¹

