
PROTECTION OF HUMAN SUBJECTS FROM RESEARCH RISK

1. Risks to Human Subjects

a. Human Subjects Involvement, Characteristics and Design

We will be studying family caregivers/legal guardians of children ages ≥1 to <18 years with rare diseases who are unable to participate in health care decision making; and retrieving protected health information on the children from the electronic health record (EHR). No data will be collected directly from the children, but PHI will be collected from the EHR.

Children's National Health System serves approximately 2,189 children who meet eligibility criteria, including children with Leukodystrophies; Intestinal Failure/Short Bowel Syndrome/Liver failure; Pediatric Cardiomyopathies; Organic Acidemias; Renal Failure in need of Renal Replacement Therapy (Dialysis and kidney transplants); Rare clotting disorders; Hemophilia A inhibitor, Severe. Our site has a history of successful research.

We will recruit for approximately twelve months until we enroll *30* family caregiver/child dyads who after completion of the baseline questionnaires will be randomized at a ratio of 1:1 into either the 3-session FACE-Rare Intervention Group (n=15 dyads) or Treatment as Usual Control Group (n = 15 dyads) with the goal of obtaining data from conservatively 21 dyads at 3 month post-intervention for statistical analysis. We have not had differential attrition in our earlier studies, as discussed in

Research Strategy. We estimate that approximately 43% of the sample will be African-American. To achieve our enrollment goal of 30 families, we estimate based on our previous studies that we will need to approach 62 families, which should be easily accomplished with the potentially available study population. Post-intervention questionnaires to asses study outcomes will be administered at 3-months post-intervention.

The current R21 proposal has received approval from Children's National's IRB, the IRB. The participant eligibility criteria have been developed with careful consideration to ensure the safety of the study participants.

Participant Eligibility Criteria

Child Inclusion Criteria:

- Diagnosed with a rare disease;
- Ages ≥1 year <18 years; no infants under the age of 1 year are included;*
- Not in foster care;
- Unable to participate in health care decision making, e.g. due to developmental delay (IQ <70), neuromuscular disorder with no communication device, under age 7;
- Waiver of assent from the legal guardian;

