Recruitment Procedures: We will utilize a three-step recruitment procedure that ensures involvement of the health care provider or medical care team to reduce the potential burden to families. To minimize gatekeeper bias, prior to study initiation, we will conduct primary care provider and healthcare team educational forums to discuss the study and address the legitimate reasons for providers to refuse approach. The study team at each site will identify potential patients through review of future appointments. First, the study team will identify potential patients through review of future appointments. Second, the health care provider will confirm eligibility criteria, e.g. patient does have a rare diagnosis and the condition is not a result of prematurity, such as in pulmonary hypertension. The health care provider will let the study team know if there is a reason not to approach the family. Third, a trained member of the study team will approach the family by email and/or telephone, and/or text, as long as COVID-19 prevents face-to-face approaches. Eligible families will be approached until 30 eligible dyads are enrolled. The selection, roles, responsibilities, and preparation of families are detailed in the 3-day Facilitator Training outlined. [name] and colleagues are currently collaborating on a study that uses a similar procedure and have found it to be successful, i.e. not burdensome to the family caregiver.

Children's National has a history of success in recruiting children and families for participation in research studies. Currently, Children's National is running two clinical trials. We are especially sensitive to the distress of families of children living with rare diseases and to recruitment during the end-of-life. For this reason we will maintain the involvement of a Community Advisory Board of Families of Children with Rare Diseases and NORD throughout the study. See **Overall Structure of Study Team**. We will generate a list of potentially eligible participants and follow the procedures described in **Recruitment and Enrollment Plan**.

Attrition: See **Approach** for data on attrition. In the PI's judgment, Children's National has such low attrition because patients form strong attachment bonds with the clinical and research staff, a "positive institutional transference" ([name]. personal communication, former director of the Family Research Center at George Washington University).

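### The 32 families to approach in D.2.a yield about 16 dyads at the section's own agreement rate; evaluable N is both 25-26 and 21; and the sufficiency of 30 dyads is not shown for quality of life

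*Combined protocol and SAP*

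**What the plan says.** **Families to approach.** In D.2.a (Study Site), "investigators estimate 50% of families approached will agree to enroll, and 1% will be ineligible at secondary screening". The section then concludes: "So to achieve our randomization goal of 30 family/child dyads investigators will need to approach 32 families, which is realistic". The same paragraph puts enrolment at the site at 32 dyads, whereas D.1 enrols and randomizes 30. Protection of Human Subjects, section 1.a, also recruits until 30 dyads are enrolled, but there "we estimate based on our previous studies that we will need to approach 62 families". Its Recruitment Procedures add: "Eligible families will be approached until 30 eligible dyads are enrolled".

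**Evaluable dyads.** D.4 sets attrition at 15% and calls that conservative. The Power & Sample Size Consideration in D.9 follows it: "With attrition at 15%, 25-26 dyads will be available at 3-months post-intervention". Human Subjects 1.a aims for 21 dyads at the same time point and calls that conservative too.

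**Adequacy of 30.** D.1 sends the reader to the power analysis for the rationale. That paragraph in D.9 says, on the strength of previous FACE research, that 30 dyads suffice to find statistically and clinically meaningful differences and to supply an effect size for the R01. It names no endpoint, effect, SD, power or interval width, and goes on to say that in a small sample the power may be in question. Under Aim 1, D.9 plans a between-group t-test on the change in each QoL measure. It takes the standardized outcome mean difference as the effect size for the R01, and also describes a standardized slope net of age, gender and race.

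**The concern.** The number to approach is presented as following from the two rates just before it, and it does not. Someone planning recruitment from D.2.a would expect about half the approaches that the assumptions require, and the document gives two answers to one question.

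The two evaluable numbers imply different precision, and nothing says which one the analysis rests on or that 21 is a floor.

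The sufficiency sentence matters most for interpretation. A stated purpose of the pilot is to estimate an effect size for a later trial, so the relevant criterion is how precisely that effect will be estimated. The plan does not say. Without that, a reader cannot tell whether sufficiency is meant for QoL, for document completion, or for both.

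**Working it through.** **1. Approaches.** Inputs from D.2.a: goal 30, agreement 0.50, ineligible 0.01.

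- Trying to reproduce 32: 30/0.99 = 30.3, so 31. Only leaving out the 50% step comes near the stated figure.
- Needed: 30/(0.5 × 0.99) = 60.6, so 61. Other ways of combining the rates give 60 (30/0.5) to 62 (30/(0.5 − 0.01) = 61.2, rounded up).
- Yield of 32: 32 × 0.5 × 0.99 = 15.8 dyads.
- Yield of 62: 62 × 0.5 × 0.99 = 30.7, so the human-subjects figure is consistent with the rates.
- Agreement needed for 30 from 32: 30/(32 × 0.99) = 0.947.
- If 32 enrolled dyads are intended: 32/0.5 = 64 approaches.

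**2. Evaluable N.** 30 × 0.85 = 25.5, which reproduces 25-26. For the other figure, 21/30 = 70%, a 30% loss, which 15% attrition does not give.

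**3. QoL.** The two-sided 0.05 level is taken from the model inference in D.9; no level is stated for the t-test itself. Assumed here, because the plan gives none: 80% power, arms of 13/13 or 11/10, and a pre-post correlation r.

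- Detectable difference δ in change-score SD: solve noncentral-t power = 0.80 with noncentrality δ/√(1/n₁ + 1/n₂) and N − 2 degrees of freedom.
- In outcome SD, with equal variances: δ × √(2(1 − r)).
- 95% half-width of the unadjusted standardized difference d: 1.96 × √(1/n₁ + 1/n₂ + d²/(2N)).
- With baseline adjustment, near zero effect: half-width at d = 0 times √(1 − r²).

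| | 26 dyads (13/13) | 21 dyads (11/10) |
|---|---|---|
| Detectable, change-score SD | 1.15 | 1.29 |
| Same, outcome SD at r = 0.3 / 0.5 / 0.8 | 1.36 / 1.15 / 0.72 | 1.53 / 1.29 / 0.82 |
| Half-width, unadjusted, d = 0 | 0.77 | 0.86 |
| Half-width, unadjusted, d = 0.8 | 0.80 | 0.89 |
| Half-width, baseline-adjusted, r = 0.5 | 0.67 | 0.74 |
| Half-width, baseline-adjusted, r = 0.8 | 0.46 | 0.51 |

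At 25 dyads (13/12) the detectable difference is 1.17. With the t quantile instead of 1.96, the half-width at d = 0 is 0.81 (26) or 0.91 (21).

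For illustration, an observed difference of 0.5 SD would have exact 95% limits of −0.29 to 1.28 (26 dyads) or −0.38 to 1.36 (21 dyads). At 80% power and two-sided 0.05, a later trial needs 64 per arm for 0.5 SD but only 10-11 per arm at those upper limits.

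**4. Document completion.** The only prior completion rates given with a named endpoint are in A.2.a: 91% versus 15% for advance directives among African-Americans living with HIV. If they applied here, the exact two-sided Fisher test would have power 0.99 (13/13) or 0.97 (11/10).

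**The case against.** **Enrolment is protected.** A reader might infer that the trial would stall near 16 dyads. The documents do not support that: recruitment runs until 30 are enrolled, Human Subjects 1.a counts about 2,189 eligible children, and D.11 has an under-enrolment plan. Nor can the 32 be spread over the twelve months in Human Subjects 1.a to argue that the planned monthly workload is half what it should be. That section plans on 62, and D.10 gives months 4-23 for recruitment and data collection together.

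**The beta test was more favourable.** A.2.b reports: "Of 9 families approached, 8 enrolled and 7 completed baseline". At 8 of 9, 32 approaches would give 32 × 8/9 × 0.99 = 28.2 dyads. At 7 of 9 completing baseline, the step after which randomization occurs, they would give 32 × 7/9 = 24.9. It is tempting to say that no acceptance rate in the documents rescues the 32. Nine families cannot carry that: the exact 95% interval for 8 of 9 is 52% to 99.7% and includes the 95% needed. The contradiction rests on D.2.a's own 50%.

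**Prior trials are cited for sufficiency.** D.9 refers to earlier FACE studies, and the titles of some in the reference list name anxiety and quality of life. They cannot be examined here, so the claim may be called not shown, but not false.

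**It is a pilot, and it says so.** The same paragraph concedes that power may be in question. That stands, but it neither withdraws nor quantifies the claim of sufficiency.

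**The widest intervals are unadjusted.** D.9 also plans a covariate-adjusted slope with a 95% credibility interval, and baseline adjustment, which it does not name, would narrow the interval as tabulated. This is right, and any stated half-width should carry the condition.

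**Use of the estimate.** A reader might infer that the pilot estimate feeds the R01 whatever the result. B.2, D.11 and the Potential Benefits section make the R01 conditional on the aims being achieved or on initial efficacy. The point about interval width does not depend on that inference.

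**Conclusion.** The point holds in three limited parts.

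- The 32 is an arithmetic error on D.2.a's own rates: about 61 approaches are needed, and 32 yield about 16 dyads. The 32 enrolled dyads in the same paragraph also conflict with 30 elsewhere. One figure may have been reused for the other, but the text does not settle that. The consequence is a wrong planning figure, not a threat to enrolment.
- Evaluable N is unreconciled: 25-26 (15% loss) against 21 (30% loss), both called conservative.
- Sufficiency of 30 dyads is not shown for the primary QoL outcomes, given the detectable differences and half-widths above. These rest on the assumed 80% power, near-equal arms and, for the half-widths, no baseline adjustment. For document completion sufficiency would hold, provided rates as far apart as 91% and 15% carry over to this population.

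**What to change.** 1. In D.2.a, change the number to approach to about 61-62, and reconcile the 32 dyads enrolled there with the 30 in D.1 and the human-subjects section. If 32 enrolled is meant, the number to approach is about 64.
2. Use one evaluable N in D.4, D.9 and Human Subjects 1.a, or label 21 as a floor.
3. Replace the general sufficiency sentence in D.9 with one limited by endpoint. State that the QoL outcomes are sized for estimation, and give the expected 95% half-width at the chosen evaluable N: about 0.8 SD for 26 dyads or 0.87 SD for 21, marked as unadjusted. Label any power or correlation as an assumption. If sufficiency is kept for document completion, state the assumed rate in each arm.

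The cost is wording only, with no added participants, procedures or analyses. The drawback is that the stated figures become less favourable.
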